4.1.4 Follow-Up Phase (End-Of-Study)

The Follow-up Phase will begin once a patient discontinues study drug or completes the Treatment Phase. The follow-up phase will continue until 28 days after last dose, loss to follow up, withdrawal of consent for study participation, or end of the study, whichever occurs earlier. A follow-up will be conducted 28 days after the EOT visit via a phone call. This will be considered as End-of-Study Visit. Every effort should be made to conduct the End-of-Study Visit.

Patients who are observed to receive clinical benefit from Acalabrutinib after completion of treatment phase, may continue to receive Acalabrutinib, if in the opinion of their treating physician they are continuing to derive clinical benefit from continued treatment or have not progressed clinically. The details on “Post-Trial Access” are provided in section 1.2.

For details on treatments given during the study, refer Section 6.1 Treatments Administered.

For details on what is included in the efficacy and safety endpoints, refer Section 3 and 8.

4.2 Scientific rationale for study design

The present study will be conducted to assess the safety and efficacy of Acalabrutinib in the Indian population of CLL/SLL and MCL. The efficacy and safety of Acalabrutinib 100 mg BID dose is established in CLL/SLL and refractory & relapsed MCL patients for 6 cycles (refer Section 2). Hence the present phase IV trial is planned to assess the safety and efficacy of Acalabrutinib 100 mg BID monotherapy for a treatment period of 168 days in Indian patients.

In the combined safety database with Acalabrutinib monotherapy, the commonest adverse events in patients receiving Acalabrutinib monotherapy as a treatment for haematological malignancies are related to blood and lymphatic system disorders, cardiac disorders, nervous system disorders, and gastrointestinal disorders. The current phase IV trial includes a treatment phase of 168 days, which would enable us to detect the incidence of adverse events and the objective response to treatment in an eligible Indian patient population. As the primary objective of the study will be an assessment of safety, the study design is a single arm, prospective open-label one.

The safety analysis (N = 1040) showed that the most common treatment-emergent AEs were anaemia, neutropenia, thrombocytopenia, headache, diarrhoea, bruising, rash, infections, and musculoskeletal pain.

4.3 Justification for dose

The dose used in the current study is based on the locally approved Prescribing Information.

4.4 End of study definition

The end of the study is defined as the last expected visit/contact of the last patient undergoing the study.

A patient is considered to have completed the study when he/she has completed his/her last scheduled visit or last scheduled procedure shown in the SoA

Refer Appendix A 6 for guidelines for the dissemination of study results.

5. STUDY POPULATION

Prospective approval of protocol deviations to recruitment and enrolment criteria, also known as protocol waivers or exemptions, is not permitted.

Each patient should meet all of the inclusion criteria and none of the exclusion criteria for this study in order to be assigned/randomised to study intervention. Under no circumstances can there be exceptions to this rule.

5.1 Inclusion criteria

Patients are eligible to be included in the study only if all of the following inclusion criteria and none of the exclusion criteria apply:

1. Men and Women aged 18 yrs or more.
2. Eastern Cooperative Oncology Group (ECOG) performance status of 0,1, or 2
3. Able to receive all outpatient treatments, all laboratory monitoring, and all radiologic evaluations.
4. The following laboratory parameters:
 - a. Absolute neutrophil count (ANC) ≥ 750 cells/ μL or ≥ 500 cells/ μL in patients with documented bone marrow involvement, and independent of growth factor support 07 days before the assessment
 - b. Platelet count $\geq 50,000$ cells/ μL or $\geq 30,000$ cells/ μL in patients with documented bone marrow involvement, and without transfusion support 07 days before the assessment
 - c. Aspartate transaminase (AST) and Alanine transaminase (ALT) ≤ 2.0 x ULN

- d. Total bilirubin $\leq 1.5 \times$ ULN
 - e. Estimated creatinine clearance of ≥ 30 mL/min
5. Refractory disease defined as achieving less than partial response with the most recent treatment before study entry
 6. Provision of signed, written and dated informed consent prior to any study-specific procedures
 7. The patients of either CLL or MCL:
 - a. **CLL patients:**
 - i. Treatment naïve or ≥ 1 prior systemic therapy for CLL
 - ii. Diagnosis of CD20+ CLL that meets published diagnostic criteria (Hallek et al. 2018)
 - iii. An active disease that meets ≥ 1 of the following iwCLL 2018 criteria for requiring treatment
 - 1) Evidence of progressive marrow failure as manifested by the development of, or worsening of, anaemia and/or thrombocytopenia. Cut-off levels of Hb < 10 g/dL or platelet counts $< 100 \times 10^9/L$ are generally regarded as an indication for treatment. However, in some patients, platelet counts $< 100 \times 10^9/L$ may remain stable over a long period; this situation does not automatically require therapeutic intervention.
 - 2) Massive (i.e., ≥ 6 cm below the left costal margin) or progressive or symptomatic splenomegaly.
 - 3) Massive nodes (i.e., ≥ 10 cm in longest diameter) or progressive or symptomatic lymphadenopathy.
 - 4) Progressive lymphocytosis with an increase of $\geq 50\%$ over a 2-months period or lymphocyte doubling time (LDT) in < 6 months. LDT can be obtained by linear regression extrapolation of absolute lymphocyte counts obtained at intervals of 2 weeks over an observation period of 2 to 3 months; patients with initial blood lymphocyte counts $< 30 \times 10^9/L$ may require a longer observation period to determine the LDT. Factors contributing to lymphocytosis other than CLL (e.g., infections, steroid administration) should be excluded.
 - 5) Autoimmune complications, including anaemia or thrombocytopenia poorly responsive to corticosteroids.
 - 6) Symptomatic or functional extra-nodal involvement (e.g., skin, kidney, lung, spine).

7) Disease-related symptoms as defined by any of the following:

- a) Unintentional weight loss of $\geq 10\%$ within the previous 06 months.
- b) Significant fatigue (i.e., ECOG performance scale 02 or worse; cannot work or unable to perform usual activities).
- c) Fever $\geq 100.5^{\circ}\text{F}$ or 38.0°C for 02 or more weeks without evidence of infection.
- d) Night sweats for ≥ 1 month without evidence of infection.

b. MCL Patients:

- i. Confirmed MCL with translocation t(11;14) (q13;q32) and/or overexpressed cyclin D1
- ii. Measurable nodal disease (one or more lesions measuring ≥ 2 cm in the longest diameter)
- iii. Relapsed after, or were refractory to, 1-5 previous treatments

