Two cohorts of patients will be included in the current study (a) patients with CLL/SLL who are treatment naïve or have received at least one prior therapy (N= 90) and (b) patients with MCL

who have received at least one prior therapy (N= 10). Potential patients will undergo screening phase within 07 days prior to the first dose. Patients who meet the protocol-defined inclusion/exclusion criteria will be prospectively enrolled in the study.

Acalabrutinib capsules 100 mg are administered twice daily (BID) for 06 cycles, starting from Cycle 1, Day 1, and continuing up to Cycle 6, Day 28; or until study drug discontinuation due to either disease progression or, unacceptable toxicity, or other reasons, whichever occurs earlier.

Acalabrutinib will be provided by the Sponsor to patients in the Treatment Phase. The Sponsor shall also conduct laboratory investigations for safety and efficacy evaluations, including haematology, biochemistry, radiology, and electrocardiography (ECG), as mentioned in the SoA table.

Patient Population

Inclusion criteria

Patients are eligible to be included in the study only if all of the following inclusion criteria and none of the exclusion criteria apply:

1. Men and Women aged 18yrs or more.
2. Eastern Cooperative Oncology Group (ECOG) performance status of 0,1, or 2
3. Able to receive all outpatient treatments, all laboratory monitoring, and all radiologic evaluations.
4. The following laboratory parameters:
 - a. Absolute neutrophil count (ANC) ≥ 750 cells/ μ L or ≥ 500 cells/ μ L in patients with documented bone marrow involvement, and independent of growth factor support 07 days before the assessment
 - b. Platelet count $\geq 50,000$ cells/ μ L or $\geq 30,000$ cells/ μ L in patients with documented bone marrow involvement, and without transfusion support 07 days before the assessment
 - c. Aspartate transaminase (AST) and Alanine transaminase (ALT) ≤ 2.0 x ULN
 - d. Total bilirubin ≤ 1.5 x ULN
 - e. Estimated creatinine clearance of ≥ 30 mL/min
5. Refractory disease defined as achieving less than partial response with the most recent treatment within 6 months before study entry
6. Provision of signed, written and dated informed consent prior to any study-specific Procedures
7. The patients of either CLL or MCL:
 - a. **CLL patients:**
 - i. Treatment naïve or ≥ 1 prior systemic therapy for CLL
 - ii. Diagnosis of CD20+ CLL that meets published diagnostic criteria (Hallek et al. 2018)

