### 2.2.2 Inclusion Criteria

1. Men and Women aged 18yrs or more.
2. Eastern Cooperative Oncology Group (ECOG) performance status of 0,1, or 2
3. Able to receive all outPatient treatments, all laboratory monitoring, and all radiologic evaluations.
4. The following laboratory parameters:
  - a. Absolute neutrophil count (ANC)  $\geq 750$  cells/ $\mu\text{L}$  or  $\geq 500$  cells/ $\mu\text{L}$  in Patients with documented bone marrow involvement, and independent of growth factor support 07 days before the assessment
  - b. Platelet count  $\geq 50,000$  cells/ $\mu\text{L}$  or  $\geq 30,000$  cells/ $\mu\text{L}$  in Patients with documented bone marrow involvement, and without transfusion support 07 days before the assessment
  - c. Aspartate transaminase (AST) and Alanine transaminase (ALT)  $\leq 2.0 \times \text{ULN}$
  - d. Total bilirubin  $\leq 1.5 \times \text{ULN}$
  - e. Estimated creatinine clearance of  $\geq 30$  mL/min
5. Refractory disease defined as achieving less than partial response with the most recent treatment within 6 months before study entry
6. Provision of signed, written and dated informed consent prior to any study-specific Procedures
7. The Patients of either CLL or MCL:
  - a. CLL Patients:

Document Title:	Document ID:	BP04-01
Statistical Analysis Plan	Version Number:	3.1
	Effective Date:	25-Nov-2021

i. Treatment naïve or  $\geq 1$  prior systemic therapy for CLL

ii. Diagnosis of CD20+ CLL that meets published diagnostic criteria (Hallek et al. 2018)

iii. An active disease that meets  $\geq 1$  of the following iwCLL 2018 criteria for requiring treatment:

- 1) Evidence of progressive marrow failure as manifested by the development of, or worsening of, anaemia and/or thrombocytopenia. Cut-off levels of Hb  $< 10$  g/dL or platelet counts  $< 100 \times 10^9/L$  are generally regarded as an indication for treatment. However, in some Patients, platelet counts  $< 100 \times 10^9/L$  may remain stable over a long period; this situation does not automatically require therapeutic intervention.
- 2) Massive (i.e.,  $\geq 6$  cm below the left costal margin) or progressive or symptomatic splenomegaly.
- 3) Massive nodes (i.e.,  $\geq 10$  cm in longest diameter) or progressive or symptomatic lymphadenopathy.

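### Inclusion criterion 5 is listed as mandatory but, read literally, bars treatment-naive patients and those who relapsed after responding to their last treatment; its time window also differs between sections

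*Protocol*

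**What the plan says.** Protocol Section 5.1 opens with the rule "Patients are eligible to be included in the study only if all of the following inclusion criteria and none of the exclusion criteria apply". Section 5 repeats it ("Each patient should meet all of the inclusion criteria and none of the exclusion criteria"), disallows waivers, and adds "Under no circumstances can there be exceptions to this rule".

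Criterion 5 stands in that list at the same level as age, performance status and consent. It reads "Refractory disease defined as achieving less than partial response with the most recent treatment before study entry". No qualifier limits it to one disease or to previously treated patients.

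The protocol synopsis (Section 1.2) words the same item differently: "Refractory disease defined as achieving less than partial response with the most recent treatment within 6 months before study entry". SAP 2.2.2 follows the synopsis, with "most recent treatment within 6 months before study entry".

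Criterion 7 in Section 5.1 sets the disease-specific entry conditions. For CLL, 7a.i asks for "Treatment naïve or ≥ 1 prior systemic therapy for CLL". For MCL, 7b.iii asks for "Relapsed after, or were refractory to, 1-5 previous treatments".

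The primary objective, in the synopsis and in SAP 2.1.1, covers treatment-naive and relapsed/refractory CLL/SLL together with relapsed and refractory MCL. Protocol Section 4.1 defines a CLL/SLL cohort of 90, either untreated or with at least one prior therapy, and an MCL cohort of 10 with at least one prior therapy.

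**The concern.** An investigator who follows the list as written cannot enrol an untreated patient, although that patient belongs to a population named in the primary objective. An investigator who enrols the patient anyway breaches a mandatory criterion that the protocol says has no exceptions. Nothing in the text offers a third course.

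Three features make this more than untidy drafting. A patient wrongly failed at screening cannot be rescreened (Section 5.4). Ten sites are planned (synopsis), and they could resolve the conflict differently, so the mix of untreated, relapsed and refractory patients could vary by site for reasons unrelated to the disease. The SAP would not readily reveal this: adverse events (Table 14.3.1) and response (Table 14.2.1) are tabulated only for CLL/SLL, MCL and the total, and no summary of eligibility deviations is planned. In a single-arm study whose main result is the incidence of adverse events, the reader needs to know who was eligible.

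**Working it through.** No arithmetic decides this point. The check sets criterion 5, read literally, against criterion 7 for each kind of patient (assuming all other criteria are met).

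| Patient | Criterion 5, read literally | Criterion 7 | Result |
|---|---|---|---|
| CLL, treatment-naive | Cannot be met: there is no most recent treatment | Admitted by 7a.i | Contradiction |
| CLL, at least partial response to the last treatment, then relapse | Not met | Admitted by 7a.i | Contradiction |
| CLL, no partial response to the last treatment | Met, subject to the window | Admitted by 7a.i | Consistent |
| MCL, at least partial response to the last treatment, then relapse | Not met | Admitted by 7b.iii as relapsed | Contradiction |
| MCL, no partial response to the last treatment | Met, subject to the window | Admitted by 7b.iii as refractory | Consistent |

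The criterion turns on the most recent treatment only. A patient who relapsed after earlier lines but was refractory to the last one satisfies it.

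**Window.** Take a patient whose last, failed treatment fell more than 6 months before entry. That patient meets item 5 in Section 5.1 but arguably not in the synopsis or in SAP 2.2.2. The SAP Introduction lets the SAP supersede the protocol's analysis, but that does not settle an eligibility rule.

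**Evidence of intent.** The following all presuppose untreated, relapsed or non-refractory patients:
- The schedule of activities (footnote e) and Section 4.1.1 provide genetic testing specifically for untreated CLL/SLL patients.
- SAP Table 14.1.4 has Yes/No rows for any prior therapy and for being refractory to it.
- SAP Table 14.1.5 separates relapsed from refractory MCL.

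Item 5 is also phrased as a definition. Yet no section states that it is one, or limits whom it covers.

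**The plan's own figures.** Sample size is about 100 by Health Authority requirement, with no hypothesis test, so no power calculation depends on item 5. All 43 filled cells of protocol Table 8 reproduce with the Clopper-Pearson formula. With 0 events the upper limit is 1 − 0.025^(1/n), which gives 4.02% for n = 90 and 3.62% for n = 100, as printed. The wording of item 5 does not alter that table.

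**The case against.** The strongest reply is that item 5 is plainly a definition that was numbered by mistake. Its phrasing, the objective, the cohort definition, criterion 7, the genetic testing plan and the SAP tables all point that way, and most investigators would probably read it so. This stands as a reading of intent. It does not remove the problem, because the no-exceptions rule takes away the discretion a site would need to act on that reading.

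A second reply is that the analysis is protected. The Full Analysis Set is every enrolled patient who received at least one dose, it serves all safety and efficacy analyses, and there is no per-protocol set. An eligibility deviation therefore removes nobody. This stands in full.

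A third is that, if item 5 is only a definition, the window decides little about entry, since 7a.i admits any previously treated CLL and 7b.iii admits relapsed as well as refractory MCL. This also stands. The window would then mainly affect how patients are labelled in SAP Tables 14.1.4 and 14.1.5. Those labels still need one meaning.

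**Conclusion.** The contradiction is real and should be corrected. As written, a mandatory criterion bars treatment-naive patients, and those who reached at least a partial response on their last treatment and then relapsed. Criterion 7 and the stated objective include them. The only firm number is that 0 treatment-naive patients satisfy the literal text, whatever the case mix. Separately, the 6-month window appears in two of the three places where the item is given.

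A reader might infer four stronger conclusions, none of which the documents support:
- **The sponsor chose a refractory-only population.** The rest of both documents says otherwise; this is an internal inconsistency, not a design choice.
- **All relapsed patients are barred.** Only those with at least a partial response to the most recent treatment are.
- **A particular number of the 90 CLL/SLL patients is affected.** The documents give no split between untreated and previously treated patients and no share of refractory patients, so any count would be pure assumption.
- **Patients or precision are lost from the analysis.** The Full Analysis Set excludes no one for an eligibility deviation, and Table 8 is correct.

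The realistic consequences are avoidable screen failures, deviations recorded against patients the trial wants, and inconsistent practice between sites.

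**What to change.** Reconcile the protocol synopsis, protocol Section 5.1 and SAP 2.2.2 as follows:
- Take item 5 out of the numbered mandatory criteria.
- Restate it as a definition of refractory that applies only to previously treated patients. The term is used in 7b.iii and in the relapsed/refractory CLL cohort description. Criterion 7a.i does not use the word, so the definition should say explicitly that it does not restrict 7a.i.
- Use one time window, chosen by the sponsor, in all three places.
- If enrolment has begun, document how each site applied item 5 and how patients who did not meet its literal wording are classified.

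The cost is a wording change to both documents. The protocol change needs IRB/IEC approval before it is implemented (Appendix A 1). No new visits, assessments or patients are required.

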5.2 Exclusion criteria

1. Known prolymphocytic leukaemia, Central Nervous System (CNS) lymphoma or leukaemia; or known history of (or currently suspected) Richter's syndrome
2. Treatment with chemotherapy, external beam radiation therapy, anticancer antibodies, or investigational drug within 30 days of the first dose of study drug
3. Prior radio-conjugated or toxin-conjugated antibody therapy
4. Anticoagulation therapy (e.g., warfarin or equivalent vitamin K antagonists) within 07 days of the first dose of study drug.
5. Major surgery ≤ 30 days before the first dose of study drug
6. History of stroke or intracranial haemorrhage ≤ 6 months before the first dose of study drug
7. History of bleeding diathesis
8. Prior exposure to a B-cell lymphoma-2 (Bcl-2) inhibitor or B-cell receptor inhibitor like BTKIs
9. Active Cytomegalovirus (CMV) infection or serologic status reflecting active Hepatitis B or C infection, known history of infection with Human immunodeficiency virus (HIV), or any uncontrolled active systemic infection.
10. Significant cardiovascular disease such as uncontrolled or symptomatic arrhythmias, Congestive Heart Failure, or Myocardial Infarction within 6 months of screening, or

any Class 3 or 4 cardiac diseases as defined by the New York Heart Association Functional Classification, or QTcB >480 msec at screening.

11. Requiring treatment with proton-pump inhibitors (e.g., Omeprazole, Esomeprazole, Lansoprazole, Dexlansoprazole, Rabeprazole, or Pantoprazole).
12. Breastfeeding or pregnant.
13. Current life-threatening illness, medical condition, or organ system dysfunction which, in the Investigator's opinion, could have compromised the subject's safety or put the study at risk.
14. Concurrent participation in another therapeutic clinical trial.

5.3 Lifestyle restrictions

Not Applicable

5.4 Screen failures

Screen failures are defined as patients who sign the informed consent form to participate in the clinical study but are not subsequently entered in the study. A minimal set of screen failure information is required to ensure transparent reporting of screen failure patients to meet the Consolidated Standards of Reporting Trials (CONSORT) publishing requirements and to respond to queries from regulatory authorities. Minimal information includes demography, screen failure details, and eligibility criteria. The reason/s for screen failure for these patients should be recorded in the electronic Case Report Form (eCRF).

Individuals who do not meet the criteria for participation in this study (screen failure) may not be rescreened.

6. STUDY TREATMENTS

Study treatment is defined as any investigational product(s) (including marketed product, comparator, and placebo) or medical device(s) intended to be administered to a study participant according to the study protocol. Study treatment in this study refers to Acalabrutinib.

6.1 Treatments administered

Table 3: Study Treatments

	Treatment
Study treatment name:	Acalabrutinib
Dosage formulation:	Capsule
Route of administration	Per Oral (PO)

Dosing instructions:	The recommended dose is 100 mg (1 capsule) twice daily. Acalabrutinib should be swallowed whole with water at approximately the same time each day. Acalabrutinib can be taken with or without food. The capsule should not be chewed, dissolved or opened.
Packaging and labelling	Study treatment will be provided and labelled in accordance with Good Manufacturing Practice (GMP) Annex 13 and per country regulatory requirement.
Provider	AstraZeneca/ delegate will be providing the Investigational Medicinal Product (IMP) to site.

The recommended dose of Acalabrutinib is 100 mg given PO twice daily for 06 cycles (each cycle is 28 days) until disease progression or unacceptable toxicity. Dose escalation or reduction is not recommended. Dose withholding or discontinuation may be required based on individual safety and tolerability.

6.1.1 Duration of treatment

The Treatment Phase will be from the start of Cycle 1, Day 1 to end of Cycle 6, Day 28, or until study drug discontinuation due to either disease progression or unacceptable toxicity, or other reasons whichever occurs earlier, as listed in Section 7.1. as continue

